16.3.2 Interim analysis for primary endpoint

Because this study is a pilot randomized parallel group trial to look for evidence of the efficacy of PEA, no interim data analysis is planned.

16.4 Secondary/Exploratory Analysis Plans

The safety analysis dataset is defined as all eligible patients who are randomized and had at least one dose of treatment (PEA or placebo).

The efficacy analysis dataset for the secondary/exploratory analysis will be based on the CIPN20 primary endpoint analysis dataset.

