6.2 Registration Procedures

6.2.1 To register a patient, access the ACCRU web page at [REDACTED] go to the Study Resources → Application section and click on “Registration” and enter the registration application. The registration application is available 24 hours a day, 7 days a week. Back up and/or system support contact information is available on the Web site. If unable to access the Web site, email the Academic and Community Cancer Research United (ACCRU) Registration Office at [REDACTED] between the hours of 8 a.m. and 4:30 p.m. Central Time (Monday through Friday).

Instructions for the registration application are available on the above web page under the Study Resources → Application section. Please refer to the “Research Registration Application Training” or Quick Reference Guide for instructions.

Prior to initiation of protocol treatment, this process must be completed in its entirety and an ACCRU subject ID number must be available as noted in the instructions. It is the responsibility of the individual and institution registering the patient to confirm the process has been successfully completed prior to release of the study agent.

Patient registration via the registration application can be confirmed in any of the following ways:

- Contact the ACCRU Registration Officer [REDACTED] If the patient was fully registered, the ACCRU Registration Office staff can access the information from the centralized database and confirm the registration.
- Refer to the Research Registration Application training on the ACCRU website under Study Resources → Applications.

6.2.2 Prior to accepting the registration/randomization, the registration/randomization application will verify the following:

- IRB approval at the registering institution
- Patient eligibility
- Existence of a signed consent form
- Existence of a signed authorization for use and disclosure of protected health information

6.2.3 Treatment cannot begin prior to registration and must begin \leq 14 days after registration.

6.2.4 Pretreatment tests/procedures (see Section 4.0) must be completed within the guidelines specified on the test schedule.

6.2.5 Treatment on this protocol must commence at an ACCRU institution under the supervision of an oncologist.

6.2.6 Study drug is available on site.

6.2.7 Patient questionnaire booklet is available on site.

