10.5.2 Baseline and Adverse Events Evaluations

Not applicable.

10.5.3 Submit via appropriate Academic and Community Cancer Research United (ACCRU) Case Report Forms (i.e., paper or electronic, as applicable) the following AEs experienced by a patient and not specified in Section 10.5:

10.5.3.1 Grade 1 and 2 AEs deemed *possibly, probably, or definitely* related to the study treatment or procedure.

10.5.3.2 Grade 3 and 4 AEs regardless of attribution to the study treatment or procedure

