13.3 Ineligible

A patient is deemed *ineligible* if after registration, it is determined that at the time of registration, the patient did not satisfy each and every eligibility criteria for study entry.

- If the patient received treatment, the patient may continue treatment at the discretion

of the physician as long as there are no safety concerns. The patient will continue in the Active Monitoring/Treatment phase of the study, as per section 4.0 of the protocol.

- If the patient never received treatment, on-study material and the Off Treatment form must be submitted. No further data submission is necessary.

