13.5 Cancel

A patient is deemed a *cancel* if he/she is removed from the study for any reason before any study treatment is given. On-study material and the Off Treatment form must be submitted. No further data submission is necessary.

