16.2 Sample size, Accrual time and Study Duration

16.2.1 Sample size

As this is a pilot trial to estimate the efficacy of PEA, the sample size is based on feasibility considerations and estimation precision. We plan to accrue a total of 88 patients (consisting of 78 evaluable patients + 10% dropout due to cancellation or ineligibility). Based on our previous trial experience [98], by assuming the standard deviation of the 0-100 scale transformed CIPN20 change score is 15 in each treatment arm. With this assumption, 26 patients per PEA arm and 26 total patients for the combined placebo arm (pooling all patients receiving

placebo together for statistical analysis) allows estimation of the difference between two arms, of the CIPN20 score change from baseline to 8 weeks, with a 95% two-sided confidence interval width of 16.8 points.

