16.4.1 Secondary endpoint analysis

16.4.1.1 Adverse events by patient will be summarized by frequencies and severity using CTCAE v5.0. The proportion of patients who experience at least one grade 3+ adverse event (regardless of attribution) will be reported. The overall adverse event rates for grade 3 or higher adverse events will be compared across the three arms (the two PEA arms and combined placebo) using a Chi-squared or Fisher's Exact tests as appropriate.

16.4.1.2 The difference in change of QOL (Question 3 [Appendix V](#), PRO-QOL) from baseline to 8 weeks will be calculated for each patient. The mean and standard deviation of the change will be reported for each PEA arm

and the combined placebo arm. Additional analysis using data collected from the Symptom Experience Diary may be performed. For patients who go off protocol treatment before 8 weeks, the question 3 response at their final observation will be used to calculate the change. For patients who do not have any post baseline data, they will be considered to have no change from baseline.

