18.5 Supporting documentation

Upload a copy of documentation in RAVE on the Supporting Documentation Form.

Baseline: The following documents are required for diagnosis and eligibility verification: Clinic note including description of prior chemotherapy and neuropathy status. These documents should be submitted within 14 days of registration.

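### The safety dataset in section 16.4 admits only eligible patients, so adverse events in patients dosed and later ruled ineligible drop out of the planned safety analysis

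*Combined protocol and SAP*

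**What the plan says.** Section 16.4 defines the safety population: "The safety analysis dataset is defined as all eligible patients who are randomized and had at least one dose of treatment (PEA or placebo". A patient must therefore be eligible, randomized and dosed. The plan defines no other safety population.

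Section 16.4.1.1 sets out the safety analysis: adverse events by frequency and severity, then "The proportion of patients who experience at least one grade 3+ adverse event (regardless of attribution) will be reported", then a chi-squared or Fisher's exact test of grade 3 or higher rates across the two PEA arms and the combined placebo arm. It serves objective 2.2.1, safety at the two doses.

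Section 13.3 treats ineligibility as a finding made after registration about the patient's status at registration. It has a separate branch for patients who have already received treatment. Whether such a patient continues is left to the judgement "of the physician as long as there are no safety concerns. The patient will continue in the Active Monitoring/Treatment phase of the study".

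Section 13.5 deals with cancels, meaning patients "removed from the study for any reason before any study treatment is given". Section 16.2.1 plans 88 patients, "consisting of 78 evaluable patients + 10% dropout due to cancellation or ineligibility".

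**The concern.** A safety population is meant to describe what happened to the people who took the product. Whether a patient met an entry criterion has no bearing on whether an event occurred after a capsule was swallowed. Under section 16.4, a dosed patient with a severe event who is later ruled ineligible has that event collected but not counted. This sits badly with section 16.4.1.1, which reports grade 3+ events whatever their attribution and so aims at a complete count.

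The exclusion is also decided after randomization. Section 13.3 sets no time limit on the ruling, so it can come after dosing or after an event. The eligibility criteria include blood count, liver and renal limits (section 3.1.9), so some of the patients excluded could be of particular interest for safety. That last point is an inference; the documents do not say it.

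**Working it through.** **1. How each type of patient is handled**

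| Patient | Dosed | Adverse events collected | Covered by stopping rule (16.6.1) | In safety dataset (16.4) |
|---|---|---|---|---|
| Eligible, including a major violation (13.4) | Yes | Yes | Yes | Yes |
| Ineligible, treated (13.3) | Yes | Yes | Yes | **No** |
| Ineligible, never treated (13.3) | No | No | No | No |
| Cancel (13.5) | No | No | No | No |

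The second row is the problem. Section 13.3 keeps these patients in the schedule of section 4.0, which has weekly adverse event assessment. Section 10.5.3 collects "Grade 3 and 4 AEs regardless of attribution to the study treatment or procedure" with no eligibility condition. The stopping rule refers to treated patients. Only the planned analysis leaves them out.

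**2. Whether the timing allows it**

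The registration application verifies eligibility (6.2.2). The clinic note used for eligibility verification comes later: "These documents should be submitted within 14 days of registration" (18.5). On dosing, section 6.2.3 says "Treatment cannot begin prior to registration and must begin" no more than 14 days after registration. The two windows coincide, so a first dose can precede central review of the note.

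**3. How many patients**

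The plan's own figure first:

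- 78/(1 − 0.10) = 86.7, so 87; or 78 × 1.10 = 85.8, so 86. The stated 88 is within two patients of either.
- Allowance: 88 − 78 = 10, and 10/88 = 11.4%.

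The documents do not split the 10 between cancels (never dosed), ineligible patients never dosed, and ineligible patients who were dosed. If the allowance holds, the number of dosed patients left out lies between 0 and 10. It is a planning figure and does not cap what happens.

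**4. Effect of omitting one dosed patient from a group**

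Inputs: n dosed per group is 26 (evaluable, 16.2.1) to 29 (88/3 = 29.3). No grade 3+ rate is given, so 1 to 4 patients with such an event per group is assumed.

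If the omitted patient had an event, the rate goes from (k+1)/n to k/(n−1), where k is the number of patients with events who remain:

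| n | k | All dosed | After omission | Fall (points) |
|---|---|---|---|---|
| 26 | 0 | 3.8% | 0% | 3.8 |
| 27 | 0 | 3.7% | 0% | 3.7 |
| 27 | 1 | 7.4% | 3.8% | 3.6 |
| 29 | 0 | 3.4% | 0% | 3.4 |
| 29 | 3 | 13.8% | 10.7% | 3.1 |

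Exact (Clopper-Pearson) 95% intervals for the second row: 1/27 gives 0.1% to 19.0%; 0/26 gives 0% to 13.2%.

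If the omitted patient had no event, the rate rises by k/(n−1) − k/n = k/[n(n−1)], where k is now the group's number of patients with events. With n = 27 and k = 3 this is 3/702 = 0.4 points, the largest value for 0 to 3 events and 27 to 29 dosed.

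**5. Chance that at least one grade 3+ patient is omitted**

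With m dosed ineligible patients and an assumed grade 3+ risk p for each, the chance is 1 − (1 − p)^m:

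| m | p = 5% | p = 10% | p = 20% |
|---|---|---|---|
| 1 | 5% | 10% | 20% |
| 3 | 14% | 27% | 49% |
| 10 | 40% | 65% | 89% |

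**The case against.** The best defence is that this is a deliberate choice of analysis set, parallel to the eligible-only primary dataset in section 16.3.1, and that it contradicts no figure in the plan. Its practical reach is also limited. Eligibility is checked before registration is accepted, and section 3.0 allows no waivers. The note due under section 18.5 covers prior chemotherapy and neuropathy status, so late verification by that route touches only some criteria. Ineligibility is judged on status at registration and the trial is double-blind, so the documents give no reason to expect exclusions to differ by arm. With a single dosed ineligible patient, the chance of losing a severe event is only 5% to 20% under the assumed risks, and the example intervals overlap heavily. Adverse events also reach the data safety monitoring board every six months (section 16.7).

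Most of this stands, and it limits the size of the problem: the demonstrable harm is incomplete counting, with no evidence of bias between arms. It does not justify the exclusion. Section 13.3 would not need a branch for treated ineligible patients if they could not arise, and no other section returns them to the analysis. Blinding does not restore an event that was never counted.

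One further point is fair: section 16.4.1.1 does not name its dataset. The link rests on section 16.4 opening with the plan's only safety definition, and the amendment should make it explicit.

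**Conclusion.** The concern holds. Followed as written, the plan removes collected adverse events in dosed patients from the analysis of its first secondary objective. The effect is probably small overall, but it can matter for a single group. Under the assumed 26 to 29 dosed patients and 1 to 4 with a grade 3+ event per group, omitting one patient with an event costs 3.1 to 3.8 percentage points and can erase a group's only severe event. Omitting an event-free patient moves the rate by about 0.4 points at most (0 to 3 events, 27 to 29 dosed).

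The number of dosed ineligible patients and the grade 3+ risk are not in the documents, so these sizes are conditional on the stated ranges. The reading of the text does not depend on them. Participant protection, the primary estimate and the sample size are untouched. This should be corrected before the analysis.

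**What to change.** In section 16.4, delete the word eligible from the safety dataset definition, so that it covers all randomized patients who received at least one dose of PEA or placebo, whatever their eligibility status. Cancels and ineligible patients who never took a dose stay out, because the dosing condition remains. Add a sentence to section 16.4.1.1 stating that its summaries and three-arm comparison use this dataset.

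The cost is one deleted word and one added sentence. For patients who remain in active monitoring, the data are already collected under sections 13.3 and 10. Planned accrual stays at 88, and the efficacy dataset does not have to change for this correction.

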16.4.1 Secondary endpoint analysis

16.4.1.1 Adverse events by patient will be summarized by frequencies and severity using CTCAE v5.0. The proportion of patients who experience at least one grade 3+ adverse event (regardless of attribution) will be reported. The overall adverse event rates for grade 3 or higher adverse events will be compared across the three arms (the two PEA arms and combined placebo) using a Chi-squared or Fisher's Exact tests as appropriate.

16.4.1.2 The difference in change of QOL (Question 3 [Appendix V](#), PRO-QOL) from baseline to 8 weeks will be calculated for each patient. The mean and standard deviation of the change will be reported for each PEA arm

and the combined placebo arm. Additional analysis using data collected from the Symptom Experience Diary may be performed. For patients who go off protocol treatment before 8 weeks, the question 3 response at their final observation will be used to calculate the change. For patients who do not have any post baseline data, they will be considered to have no change from baseline.

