3.1 Registration -- Inclusion Criteria

- 3.1.1 Age \geq 18 years.
- 3.1.2 ECOG Performance Status 0, 1, 2 (Form available on ACCRU website).
NOTE: Patients with a history of metastatic cancer or an ECOG Performance Status of 2 must have lab work (see Section 3.1.9) completed \leq 28 days prior to registration.
- 3.1.3 Pain, numbness, tingling or other symptoms of CIPN of \geq 3 months (90 days) duration for which the patient is seeking an intervention.
- 3.1.4 Neurotoxic chemotherapy must have been completed \geq 3 months (90 days) prior to registration and there must be no further planned neurotoxic chemotherapy for $>$ 2 months after registration.
Note: The study is limited to those with taxane- and/or platinum-based neuropathy.
- 3.1.5 Patient must note tingling, numbness or pain symptoms of at least a four out of ten \leq 7 days prior to registration.
Note: On a 0-10 scale where zero was 'no problem' and ten being 'as bad a problem that could be imagined': *how much of a problem has numbness, tingling,*

and/or pain in your fingers and/or toes been in the past week? (patient verbal report utilizing question 1 in [Appendix VI “Peripheral Neuropathy Questions”](#)).

- 3.1.6 Patient must be able to speak, read and comprehend English.
- 3.1.7 For women of childbearing potential only, a negative urine or serum pregnancy test done \leq 14 days prior to registration is required.
A female of childbearing potential is a sexually mature female who: 1) has not undergone a hysterectomy or bilateral oophorectomy; or 2) has not been naturally postmenopausal for at least 12 consecutive months (i.e., has had menses at any time in the preceding 12 consecutive months).

NOTE: If the urine test cannot be confirmed as negative, a serum pregnancy test will be required.

- 3.1.8 Life expectancy \geq 6 months.
- 3.1.9 Required Initial Laboratory Values: Following completion of chemotherapy, patients must have had a CBC and serum chemistries, including the following:
 - Platelet count $> 100,000/\text{mm}^3$
 - Absolute neutrophil count (ANC) $\geq 1,000/\text{mm}^3$
 - Hemoglobin $> 11 \text{ g/dL}$
 - Serum transaminase [ALT or AST] $\leq 1.2 \times$ upper limit of normal (ULN)
 - Alkaline phosphatase $\leq 1.2 \times$ ULN
 - Serum creatinine $\leq 1.2 \times$ ULN

NOTE: Patients with a history of metastatic cancer or an ECOG Performance Status of 2 must have these labs completed \leq 28 days prior to registration.

- 3.1.10 Able to swallow oral medication.

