4.0 Test Schedule

	Screening			Active Monitoring Phase	
	Prior to Registration			Prior to Start of Treatment (baseline)	End of each weekly cycle (for 8 weeks)
	≤ 28 Days	≤ 14 Days	≤ 7 Days		
Tests & Observations					
History	X				
CBC and serum chemistries, including serum transaminase [ALT or AST], alkaline phosphatase and Cr ¹	X ¹				
ECOG PS	X				
Laboratory Studies					
Serum or Urine HCG ²		X ²			
Patient reported measures**					
EORTC QLQ-CIPN 20 (Appendix II)				X	X
Patient Global Impression of Change (Appendix III)					X
Chemotherapy-Induced Peripheral Neuropathy Assessment Tool (Appendix IV)				X	X

Symptom experience diary (Appendix V)				X	X
Peripheral Neuropathy Question (Appendix VI)			X ⁴	X	X
Cognitive Functioning Assessment (Appendix VII)				X	X
Adverse Event Assessment ³					X ³
Nurse telephone contact ³ (Appendix VIII)					X ³

** To be completed using paper booklets. Patient questionnaire booklets are to be available prior to the registration of any patients. The booklet order form is located on the ACCRU website under 'Manuals and Forms'. Patients are to complete these booklets prior to the end of each week of treatment (See Section 7.2). See appropriate Appendices for samples of the booklets.

1 This blood testing is required within the 28 days prior to registration if the patient has a history of metastatic cancer or currently has an ECOG Performance Score of 2 (See eligibility criteria 3.1.9). For patients who do not have a history of metastatic cancer or a current ECOG Performance Score of 2, this blood testing is to have been completed after the patient finished their chemotherapy per eligibility criteria 3.1.4.

2 For women of childbearing potential. Must be done \leq 14 days prior to registration.

3 Nurse/Research Coordinator will contact the patient at the end of each weekly cycle (+ 2 days) to remind the patient to complete questionnaires, answer questions, and to query adverse events.

4 To be collected orally (per eligibility criteria 3.1.5) and the response will be documented on the eligibility checklist and in the clinic note (per section 18.5).

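### With no CTCAE grade recorded before the first dose, the grade 3+ adverse-event rate cannot be reliably confined to events that are new or worse than at entry

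*Combined protocol and SAP*

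**What the plan says.** - **Baseline.** Section 10.5.2, headed "Baseline and Adverse Events Evaluations", contains only the words "Not applicable".
- **Timing.** In the Section 4.0 test schedule, the adverse-event row is marked only for the end of each weekly cycle; the screening and baseline columns are blank. Footnote 3 places the staff call "at the end of each weekly cycle (+ 2 days) to remind the patient to complete questionnaires, answer questions, and to query adverse events".
- **Reporting.** Section 10.5.3.2 requires submission of "Grade 3 and 4 AEs regardless of attribution to the study treatment or procedure". Section 10.5.3.1 asks for grade 1 and 2 events only when they are judged at least possibly related.
- **Analysis.** Section 16.4.1.1 says: "The proportion of patients who experience at least one grade 3+ adverse event (regardless of attribution) will be reported". It continues: "The overall adverse event rates for grade 3 or higher adverse events will be compared across the three arms", by a chi-squared or Fisher's exact test. The safety set in Section 16.4 depends on eligibility, randomization and at least one dose; it sets no condition on when an event began.
- **Definition.** Section 10.0 ties an adverse event to the use of a drug, whether or not the drug is thought to be the cause. It does not mention onset or baseline status.
- **Population.** Section 3.1.5 reads: "Patient must note tingling, numbness or pain symptoms of at least a four out of ten". Section 3.1.3 requires symptoms for at least 90 days. Neither sets an upper limit on severity.

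**The concern.** A grade 3+ rate that ignores attribution is normally made interpretable by a baseline grade or by a rule limiting the count to events that begin or worsen after the first dose. This plan has neither. It also recruits patients who all carry a symptom that CTCAE grades, after chemotherapy that may have left others.

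At stake is the only formal between-arm safety test in the plan. Safety is the first secondary objective (2.2.1), secondary endpoints are to be reported on the public registry (16.7), and the trial exists to inform a phase III design (2.1). If the grade 3+ rate partly reflects symptoms present at entry, its absolute level would mislead the phase III team.

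**Working it through.** **1. Can new and pre-existing events be told apart?** These are the pre-dose sources in the plan and what each supplies.

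| Source | Content | CTCAE grade? |
|---|---|---|
| 10.5.2 | Nothing | No |
| 4.0, screening | History, ECOG status | No |
| 4.0, baseline booklet | CIPN20, CIPN Assessment Tool, neuropathy questions, cognitive items | No |
| Appendix V, baseline diary | Nausea/vomiting, diarrhea, quality of life | No |
| 18.5 | Clinic note covering prior chemotherapy and neuropathy status | Not required |

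No rule links any of these to a CTCAE grade or to the adverse-event count. The call guide in Appendix VIII lists type, severity and attribution of side effects. It names neither onset date nor presence before treatment, though its list is not exhaustive. Because 10.5.3.1 collects low-grade events only when related, a grade 2 symptom at entry need leave no CTCAE record. A later move to grade 3 could then not be shown from the adverse-event data alone.

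**2. Size.** The plan gives no expected grade 3+ rate, power or sample size for this comparison, so there is no figure to reproduce. The one usable input is 26 patients per analysis group (16.2.1). The rest is assumed:

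- b = proportion with a grade 3 condition at entry, all of them counted: 5% to 20%
- e = true rate of new or worsened grade 3+ events: 4% on placebo, 15% on PEA

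Reported rate = b + (1 − b)e. Reported difference = (1 − b)(e₁ − e₀).

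| b | Carried-in patients of 26 | Placebo rate | PEA rate | Difference |
|---|---|---|---|---|
| 0 | 0 | 4.0% | 15.0% | 11.0 points |
| 5% | 26 × 0.05 = 1.3 | 0.05 + 0.95 × 0.04 = 8.8% | 0.05 + 0.95 × 0.15 = 19.25% | 0.95 × 11 = 10.45 points |
| 20% | 26 × 0.20 = 5.2 | 0.20 + 0.80 × 0.04 = 23.2% | 0.20 + 0.80 × 0.15 = 32.0% | 0.80 × 11 = 8.8 points |

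The placebo rate is multiplied by 2.2 to 5.8 (8.8/4 and 23.2/4). The difference loses only 0.55 to 2.2 points.

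**3. Effect on the test.** Exact power of a pairwise two-sided Fisher test with 26 per group is shown below. The 0.05 level is assumed, since the plan states none, and the plan's own test is across three arms.

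| True rates | b = 0 | b = 5% | b = 10% | b = 20% |
|---|---|---|---|---|
| 2% v 20% | 0.334 | 0.275 | 0.205 | 0.132 |
| 2% v 30% | 0.748 | 0.582 | 0.447 | 0.309 |

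Power falls faster than the difference because the background events also add variance. Even with no carry-in, an 18-point excess would be detected only about one time in three.

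**4. Direction.** Entry status precedes randomization, so b is equal across arms in expectation. Chance imbalance remains: under simple randomization, the standard deviation of the difference in carried-in counts between two groups of 26 is √(2 × 26 × b(1 − b)). That is 1.6 patients at b = 5% and 2.9 at b = 20%.

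**The case against.** The strongest reply is that the plan does not require entry neuropathy to be counted. Section 10.0 ties an adverse event to drug use, and neuropathy that is unchanged since before the first capsule fits that poorly. The weekly call solicits nausea, vomiting and diarrhea, and nothing tells staff to grade neuropathy by CTCAE, which is followed by separate efficacy questionnaires. This stands. A reader might infer that every patient with grade 3 neuropathy at entry must enter the count at week 1; the documents do not say so. They leave the boundary unwritten, which makes the count depend on site practice.

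A second reply is that pre-dose information exists. Also true: the questionnaires, history and clinic note would let an analyst query a reported grade 3 neuropathy, and the baseline diary covers the symptoms the call solicits. It would therefore be too strong to say that worsening can never be shown. But the check is partial, and the plan does not prescribe it.

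Third, a reader might infer that safety monitoring as a whole is compromised. It is not. The stopping rule in 16.6.1 needs at least possible attribution, so it is largely unaffected. Section 16.4.1.1 also summarizes events by frequency and severity, and attribution is recorded, so a summary restricted to related events is available.

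Finally, eligibility narrows other sources of carry-in through the laboratory limits, ECOG 0-2 and the exclusion of residual cancer. It does not cap neuropathy severity.

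**Conclusion.** The point holds as a possibility that the plan leaves open, not as a certain error. The plan expressly opts out of the baseline grade needed to separate new from pre-existing grade 3+ events, then reports and tests a rate that makes no such separation.

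The main exposure is the absolute rate, which could read 8.8-23.2% where the truth is 4%. Dilution of an 11-point excess to 10.5-8.8 points is modest. These figures assume that 5-20% of patients have a grade 3 condition at entry, that all of them are counted, and that they are counted equally often in each arm. The documents give no entry rate, and the 4/10 threshold is not mapped to any CTCAE grade, so the true size is unknown and could be near zero if sites leave such findings out.

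A reader might infer a bias for or against PEA. Randomization gives no reason to expect one from entry status, although chance imbalance is possible with groups of 26. The primary endpoint is not affected.

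**What to change.** **Section 10.5.2 and the test schedule.** Replace the present entry with a requirement to record, before the first dose, the CTCAE v5.0 grade of peripheral sensory neuropathy, peripheral motor neuropathy, nausea, vomiting, diarrhea and any other ongoing symptom. Grading every event named in 15.1.7 is unnecessary. Add the matching mark to the baseline column in Section 4.0, and date the form, since treatment may start up to 14 days after registration (6.2.3).

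**Section 16.4.1.1.** Define the grade 3+ endpoint as events that start, or increase in grade, after the first dose. List events already present at baseline separately by arm.

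**Cost.** One short baseline form, a few minutes at the registration visit and a sentence or two in the analysis section. No new procedure is needed. For patients already treated without a baseline grade, the history, clinic note and baseline questionnaires can be used to flag likely pre-existing events, with that limitation stated in the report.
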